| TITLE OF THE STUDY: VisuMax femtosecond laser small incision lenticule extraction (SMILE) for the correction of high myopia. | |
| DEVELOPMENT PHASE: Investigator Initiated Trial (IIT) | |
| METHODOLOGY: Prospective, single-center, non-randomized, including primary and secondary endpoints | |
| GENERAL OBJECTIVE: The objective of this clinical trial is to evaluate the safety and effectiveness of the Carl Zeiss Meditec VisuMax™ femtosecond laser small incision lenticule extraction (SMILE) procedure for the reduction or elimination of myopia for manifest refraction spherical equivalent (MRSE) up to -14.00 D with maximum 7.00 D cylinder (myopia with or without astigmatism). | |
| NUMBER OF PATIENTS: 187 eyes | |
| INVESTIGATIONAL DEVICE : VisuMax femtosecond laser | |
| DURATION OF TREATMENT: The overall treatment phase for all patients will be about 24 months | |
| DURATION OF FOLLOW-UP FOR EACH PATIENT: 1 year | |
| START OF STUDY: February 2016 | |
| Interim Report: February 2017 | |
| FINAL REPORT: September 2019 | |
| MAIN INCLUSION CRITERIA: - Patients with high myopia with or without astigmatism for MRSE between -9.00 D and -14.00 D, who would like to undergo SMILE surgery with the VisuMax femtosecond laser system | |
| MAIN EXCLUSION CRITERIA: - Patients, who are not medically suitable for laser refractive surgery | |

LIST OF ABBREVIATIONS AND DEFINITIONS

| | |
|----------------------|---|
| Astigmatism | Refractive error, caused by an irregularly shaped cornea with one meridian being significantly more curved than the meridian perpendicular to it |
| Cap | Corneal tissue above the refractive lenticule that remains intact except for a small incision through which the refractive lenticule is removed |
| CDVA | Corrected Distance Visual Acuity |
| CE | Conformité Européenne |
| CZM | Carl Zeiss Meditec |
| D | Diopter |
| eCRF | electronic Case Report Form |
| EMR | Electronic Medical Record |
| GCP | Good Clinical Practice |
| HOA | Higher Order Aberrations |
| LASIK | Laser in situ Keratomileusis |
| MPG | Medizinproduktgesetz - Medical Devices Act |
| Myopia | Nearsighted or shortsighted |
| MRSE | Mean Refractive Spherical Equivalent (=sphere + cylinder/2) |
| PRK | Photorefractive Keratectomy |
| RST | Residual Stromal Thickness |
| SAE | Serious Adverse Event |
| SLT | Sub-lenticule Thickness |
| SMILE | Small Incision Lenticule Extraction |
| Spherical Aberration | Aberration, where parallel light rays do not have the same focus after they pass through an optical system In the Zernike Polynomial expansion the coefficient is: Z_4^0 |
| TUST | Total Uncut Stromal Thickness |
| UDVA | Uncorrected Distance Visual Acuity |

1 BACKGROUND INFORMATION

1.1 INVESTIGATIONAL DEVICE

The following devices and software options have to be used during the clinical investigation:

→VisuMax femtosecond laser (device) for therapeutic and refractive applications of corneal surgery.¹

The VisuMax has CE approval for treating myopia and myopia with astigmatism up to -10D sphere and 5D cylinder.²

The focus of this Investigator Initiated Trial is on the treatment option SMILE for high myopia and high myopia with astigmatism up to -14D spherical equivalent and 7D cylinder.

→SMILE treatment option (software-license)

2.0 STUDY RATIONALE

Laser refractive surgery has been established for more than 25 years^{3, 4} for the treatment of low to high myopia. While PRK was defined as a first generation of laser refractive surgery, LASIK was the second generation. In the 1990s many studies were published reporting PRK and LASIK correction of very high myopia (up to -32.00 D in some cases),⁵⁻¹⁰ however, these early treatments were associated with low predictability, significant regression of the refractive correction, and induced night vision disturbances.¹¹⁻¹³ During this period, it was found that these issues were for the most part due to the use of small optical zones and minimal transition zones,^{14, 15} as well as the non-aspheric nature of the Munnerlyn ablation profiles that were resulting in high induction of spherical aberration¹⁶ and producing serious changes in night vision (glare and halos) and loss of contrast sensitivity. The introduction of aspheric profiles in the early 2000s resulted in significant reduction of the induction of spherical aberration along with improved safety in contrast sensitivity.^{17, 18} At around the same time, many studies investigated the influence of the optical zone diameter, and demonstrated that small optical zones were one of the major risk factors for night vision complaints.¹⁹⁻²¹ It was also shown that larger optical zones significantly reduced the amount of aberrations post-operatively and provided better outcomes and greater stability. Recent studies have shown that treatment of high myopia (<-10 D) using larger optical zones and aspheric profiles is safe and effective.^{3, 4, 22-25}

| | | |
|------------|-------------|---------------------------|
| 01/02/2016 | Version 3.0 | CONFIDENTIAL Page 7/28 |
|------------|-------------|---------------------------|

A further concern of treating high level of myopia was the increased risk of keratectasia. Keratectasia can be induced either by excessive tissue removal or by tissue removal in an already ectatic cornea such as a keratoconic cornea. It has now been established and is accepted in the community of refractive surgeons that the residual stromal thickness of uncut stroma under a LASIK flap should be no thinner than 250 µm and the total uncut stromal thickness for a postop PRK treatment should be no thinner than 300 µm. The major contributor to the risk of excessive keratectomy is the variation in flap thickness.²⁶⁻²⁸ Improvements in microkeratome design and the introduction of femtosecond lasers for flap creation have significantly reduced the variation in flap thickness.²⁹⁻³² Femtosecond lasers also add the ability to create very thin flaps (down to 80 µm using the VisuMax³³), which has further reduced the risk of leaving less than 250 µm of residual stromal thickness.

There have also been significant improvements in diagnostic techniques, and a lot of effort has been directed towards improving methods of screening for keratoconus preoperatively.³⁴⁻³⁸

The combination of knowledge of safety limits, improved safety calculations and improved keratoconus screening has dramatically reduced the risk of ectasia.

SMILE, as the third generation of refractive laser surgery, performed using the VisuMax femtosecond laser system, is established for treatments of myopia and myopia with astigmatism with CE approval for sphere up to -10.00 D and cylinder up to 5.00 D.² Refractive predictability, safety and patient satisfaction after SMILE have been reported to be high and comparable to results in previous studies of femtosecond LASIK for moderate to high myopia.^{39, 40}

SMILE involves passing a dissector through a small 2–3 mm incision to separate the lenticular interfaces created by the femtosecond laser and allow the lenticule to be removed, thus eliminating the need to create a flap. This means that less anterior corneal lamellae are severed in SMILE, which has two main advantages. First, it is known that vertical cuts (e.g. flap sidecut) have more biomechanical impact than horizontal cuts. Recently, Knox Cartwright et al⁴¹ performed a study on human cadaver eyes that compared the corneal strain produced by a LASIK flap, a sidecut only, and a delamination cut only. The authors demonstrated that the increase in strain was equivalent between a LASIK flap cut and a sidecut alone. In contrast, the increase in strain after a delamination cut only was lower than after a LASIK flap or sidecut only. Applying this finding to SMILE, since no anterior corneal sidecut is created, there will be a reduced impact on corneal strain in SMILE compared to thin flap LASIK. Second, it is known that that the cohesive tensile strength (i.e., how strongly

| | | |
|------------|-------------|---------------------------|
| 01/02/2016 | Version 3.0 | CONFIDENTIAL Page 8/28 |
|------------|-------------|---------------------------|

the stromal lamellae are held together) of the stroma decreases from anterior to posterior within the central corneal region, with the anterior 40% stromal lamellae being the strongest region of the cornea, whereas the posterior 60% of the stroma are at least 50% weaker.^{42, 43} In addition to cohesive tensile strength, tangential tensile strength (i.e., stiffness along the stromal lamellae) and shear strength (i.e., resistance to torsional forces) have both been found to vary with depth in the stroma. Kohlhaas et al.⁴⁴ and Scarcelli et al.⁴³ found that the tangential tensile strength was greater for the anterior stroma than posterior stroma, each using different methodology. Applying this knowledge to SMILE, since the anterior stroma remains uncut, the strongest part of the stroma continues to contribute to the strength of the cornea postoperatively, in contrast to both photorefractive keratectomy (PRK) and LASIK where the strongest anterior stroma is affected.

In order to model these differences in corneal tensile strength between LASIK and SMILE, we recently developed a mathematical model based directly on the Randleman⁴² depth dependent tensile strength data to compare the postoperative tensile strength between PRK, LASIK and SMILE.⁴⁵ The total tensile strength after PRK, LASIK and SMILE was calculated as the area under the regression line for the depths of the stroma that remain uncut in each type of procedure. The model demonstrated that the postoperative tensile strength would be greater after SMILE than after both PRK and LASIK.

In summary, considering the safety of subtractive corneal refractive surgical procedures in terms of tensile strength represents a paradigm shift away from classical residual stromal thickness limits. Ideally, a parameter such as total tensile strength, which takes the nonlinearity of the strength of the stroma into account, seems more appropriate than residual stromal thickness as the limiting factor for corneal refractive surgery. At least, a simpler and more conservative way of modelling the total postoperative tensile strength is to calculate the Total Uncut Stromal Thickness (TUST). In SMILE, the TUST is the addition of the uncut stromal thickness in the cap and the Sub-Lenticule Thickness (SLT) defined as the remaining stromal thickness below the lenticule. This is different to LASIK, where only the RST is taken into account as all lamellae in the anterior stroma are cut as a result of the flap.

Knowing that a RST of 250 µm is safe for LASIK, the minimum total uncut stromal thickness (TUST) was conservatively set to 300 µm for the present study, with a minimum sub-lenticule thickness of 220 µm.

As described earlier, the results of SMILE up to -10.00 D have been shown to be similar to those achieved by LASIK. However, there is reason to expect the results of SMILE to be superior to LASIK for very high myopia because all of the potential errors associated with

| | | |
|------------|-------------|---------------------------|
| 01/02/2016 | Version 3.0 | CONFIDENTIAL Page 9/28 |
|------------|-------------|---------------------------|

excimer laser ablation are avoided, such as stromal hydration,⁴⁶ laser fluence projection and reflection losses,^{47, 48} and other environmental factors.⁴⁹ In SMILE, the tissue removal is defined only by the accuracy of the femtosecond laser, which is not affected by any changes in environmental conditions. Therefore, the accuracy of the lenticule interfaces will be independent of the overall thickness of the lenticule (i.e. the amount of correction), meaning that the potential error due to the surgery will be the same for low and high myopia.

These factors should also reduce the induction of higher order aberrations, particularly spherical aberration, compared to LASIK as has been shown for moderate myopia.^{50, 51} The induction of spherical aberration should be reduced both by the increased contribution of the anterior stroma thereby reducing the peripheral stromal expansion postoperatively,^{52, 53} as well as the elimination of the laser fluence projection and reflection losses that degrade the peripheral ablation.^{47, 48}

Therefore, the introduction of SMILE has the potential to improve the outcomes of corneal refractive surgery for very high myopia in terms of accuracy, safety, and quality of vision (induction of aberrations). This study will investigate safety and effectiveness for high myopia with sphere -10.00 D or higher treated by SMILE with the VisuMax femtosecond laser system.

3.0 STUDY OBJECTIVES

The primary objective of this study is to evaluate the safety and efficacy of the Carl Zeiss Meditec VisuMax™ femtosecond laser SMILE procedure for the reduction or elimination of myopia with spherical equivalent from -9.00 D to -14.00 D with a maximum cylinder of 7.00 D (high myopia with or without astigmatism). The secondary objective of the study is to establish appropriate safety parameters for SMILE surgery given that they have been set to be the same as LASIK.

4.0 STUDY ENDPOINTS

4.1 MAIN ENDPOINT

1. Standard deviation of $SE_{postop} - SE_{target}$ at each follow-up time point (represent the scatter of the refractive outcome)
2. Difference in keratometry between the 3 months and 12 months' time points to be the same as for group of matched LASIK eyes.

| | | |
|------------|-------------|----------------------------|
| 01/02/2016 | Version 3.0 | CONFIDENTIAL Page 10/28 |
|------------|-------------|----------------------------|

4.2 SECONDARY ENDPOINTS

The secondary, descriptive endpoints will include:

3. Cumulative UDVA distribution at each time point compared to pre-operative CDVA (efficacy diagram A⁵⁴).
4. Distribution of lines difference between post-operative UDVA and pre-operative CDVA in order to normalize the improvement in visual acuity between eyes (efficacy diagram B⁵⁴).
5. Change in CDVA as a loss-of-line distribution at each time point (safety diagram C⁵⁴) including the percentage of eyes with CDVA unchanged or lines gained, and the percentage of eyes with a loss of 2 or more lines.
6. Cumulative distribution of CDVA at each time point.
7. Stability of spherical equivalent refraction (SE) (diagram F⁵⁴):
The mean and standard deviation at each time point will be calculated, as well as the percentage of eyes with a change of 0.5 D and 1.0 D between 1-month- and 3-months follow-up, and between 3-months and 12-months follow-up.
8. Predictability of spherical equivalent including linear regression analysis of achieved SE depending on attempted SE (diagram D⁵⁴).
9. Spherical equivalent refractive accuracy (diagram E⁵⁴):
Distribution of $SE_{postop} - SE_{target}$ at each follow-up time point.
10. Refractive astigmatism as a distribution of pre- and post-operative astigmatism at each follow-up time point (diagram G⁵⁴).
11. Side effects and complications at each time point (numbers and percentages) according appendix 1.
12. Standard analysis of corneal aberrations with focus on spherical aberration with ATLAS pre- versus post-operative and stability of corneal aberrations post-operative for all follow-up visits with an ATLAS.
13. Cylinder vector analysis according to the Alpins method⁵⁵ including predictability of the target induced astigmatism vector relative to the surgically induced astigmatism vector, and the distribution of the angle of error (angle between the target induced astigmatism vector and surgically induced astigmatism vector) (diagrams H and I⁵⁴).

| | | |
|------------|-------------|--------------|
| 01/02/2016 | Version 3.0 | CONFIDENTIAL |
| | | Page 11/28 |

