7.2 OPERATIVE PROCEDURES

The treatment protocol will provide information as described in the schedule of assessments and as usually done in daily practice for SMILE.

Schedule of Assessments

| Examination | preOP | OP | 1d | 1m | 3m | 12m |
|---|-----------|----|--------|----------|-----------|------------|
| Days to treatment | -60 to -1 | | 1 to 2 | 21 to 42 | 75 to 110 | 305 to 440 |
| Patient Demographics, medical history | X | | | | | |
| Informed consent | X | | | | | |
| Pupil diameter (Procyon) | X | | | | | |
| Intraocular pressure (IOP) (Goldmann) | X | | | | | X |
| Fundus examination | X | | | | | X |
| Cycloplegic refraction | X | | | | | |
| Subjective refraction | X | | X | X | X | X |
| Contrast sensitivity | X | | | | X | X |
| Slitlamp examination | X | X | X | X | X | X |
| Corneal topography and wavefront (ATLAS) | X | | X | X | X | X |
| Corneal tomography (Pentacam) | X | | | | X | X |
| Wavefront (WASCA) | X | | | | X | X |
| Optical quality (HD Analyzer) | X | | | | X | X |
| Corneal & epithelial thickness (RTVue OCT) | X | | | | X | X |
| Ocular Response Analyzer | X | | | | | X |
| Severe side effects / complications | | X | X | X | X | X |
| UDVA | X | | X | X | X | X |
| CDVA | X | | | X | X | X |
| Patient questionnaire for night vision disturbances | X | | | | X | X |
| Light Disturbance Analysis (LDA) | X | | | | X | X |
| Treatment protocol and videos | | X | | | | |
| Laser settings | | X | | | | |

Note: All described examinations are usually done in daily routine practice.

| | | |
|------------|-------------|--------------|
| 01/02/2016 | Version 3.0 | CONFIDENTIAL |
| | | Page 15/28 |

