8.0 AVERSE EVENT REPORTING

DEFINTION OF AN ADVERSE EVENT (AE)

An AE is any unfavourable and unintended sign (including an abnormal laboratory finding), symptom or disease temporally associated with the use of a medical treatment or procedure that may or may not be considered related to the medical treatment or procedure.

REPORTING OF AES

Patients will be instructed by the investigator to report the occurrence of any AE. The investigator assesses and records all AEs observed during the AE reporting period which is defined as postoperative until the end of the study. Any event considered as related to the procedure will be reported regardless of timing.

DEFINITION OF SERIOUS ADVERSE EVENT (SAE) SAES DURING STUDY PERIOD

A SAE includes any of the events listed in Table 1 below and occurring between registration and until completion of the study.

| | | |
|------------|-------------|----------------------------|
| 01/02/2016 | Version 3.0 | CONFIDENTIAL Page 16/28 |
|------------|-------------|----------------------------|

Table 1 SAE Definitions

| | Comments |
|---|--|
| Fatal | All events resulting in death |
| Life-threatening | The patient was at immediate risk of death from the event as it occurred. It does not include an event that, had it occurred in a more serious form, might have caused death |
| Requires inpatient hospitalization (> 24 hours) | Events not considered to be SAE are hospitalizations > 24 hours and occurring under the following circumstances: - elective surgery (planned before entry into the trial) - part of the normal treatment or monitoring of the trial treatment - hospitalization for social reasons (e.g. in rehabilitation home) - progressive disease |
| Prolongs hospitalization | Prolongation of an existing hospitalization |
| Disabling | Includes persistent or relevant disability or incapacity |
| Secondary malignancy | Any new malignancy other than a relapse of the current tumour |
| Congenital anomaly | Birth defect of offspring |
| Other medically significant condition | Important AEs that are not immediately life-threatening or do not result in death or hospitalization but may jeopardize the patient or may require intervention to prevent one of the other outcomes listed above |

SAEs after End of Trial Treatment

During the follow-up phase, the following events have to be reported as SAE:

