APPENDIX 1: ADVERSE EVENTS AND SERIOUS ADVERSE EVENTS REPORTING

ADVERSE EVENTS¹

The following adverse events, although not an all-inclusive list, should be considered to be reportable.

Any adverse event (AE), whether ascribed to the surgical procedure or not, have to be identified by an updated version of the CRF.

- Diffuse lamellar keratitis (Grade 2 or above)
- Corneal infiltrate or ulcer
- Corneal epithelial defect only at 1 month or later
- Corneal edema (Grade 2 or above) only at 1 month or later
- Epithelium in the interface with loss of 2 lines or more CDVA
- Decrease in CDVA of greater than or equal to 2 lines at 3 months or later
- Any other vision-threatening event
- Ocular penetration
- Ectasia
- Others (describe)

Additional possible adverse events:

- Foreign body sensation only at 3 months or later
- Pain at 3 months or later
- Ghost/double images in the operative eye
- Dry eye at 6 months or later
- Significant night vision disturbances at 6 months or later

SERIOUS ADVERSE EVENTS

Any Serious Adverse Event (SAE), whether ascribed to the surgical procedure or not, will be communicated promptly (within 24 hours after knowledge) according to local regulations and GCP guidelines.

- death
- life-threatening illness or injury

¹ American National Standard ANSI Z80.11-2007

| | | |
|------------|-------------|--------------|
| 01/02/2016 | Version 3.0 | CONFIDENTIAL |
| | | Page 23/28 |

- a permanent impairment of a body structure or a body function
- in-patient hospitalization or prolongation of existing hospitalization
- medical or surgical intervention to prevent life threatening illness or injury or permanent impairment to a body structure or a body function
- fetal distress, fetal death or a congenital abnormality or birth defect
- device deficiencies that might have led to a serious adverse event if a) suitable action had not been taken or b) intervention had not been made or c) if circumstances had been less fortunate

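### Endpoint 11 tabulates complications visit by visit, with no rule for adverse events recorded between visits and no cumulative per-eye incidence

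*Combined protocol and SAP*

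**What the plan says.** **The summary.** Section 4.2, item 11, lists among the descriptive secondary endpoints "Side effects and complications at each time point (numbers and percentages) according appendix 1".

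**The time points.** The Schedule of Assessments in section 7.2 sets the postoperative windows, in days from treatment, at "1 to 2 | 21 to 42 | 75 to 110 | 305 to 440". These belong to the 1-day, 1-month, 3-month and 12-month visits. The complications row also marks the day of surgery, which makes five time points.

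**The recording.** Section 8.0 does not tie recording to visits. For patients: "Patients will be instructed by the investigator to report the occurrence of any AE". For the investigator: "The investigator assesses and records all AEs observed during the AE reporting period which is defined as postoperative until the end of the study". It adds: "Any event considered as related to the procedure will be reported regardless of timing".

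**The event list.** Appendix 1 restricts some events to a minimum time after surgery: corneal epithelial defect and corneal edema from 1 month, dry eye and significant night vision disturbance from 6 months. Others have no time limit. The list begins with "Diffuse lamellar keratitis (Grade 2 or above", and corneal infiltrate or ulcer and other vision-threatening events are likewise unrestricted.

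**The analysis.** Section 9.1 refers to the standard refractive-surgery reporting graphs and says nothing further about adverse events.

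**The concern.** Adverse events are collected continuously but summarised by visit, and no rule connects the two. An analyst holding the record of an acute event that began and resolved between two visits would have to decide, without guidance, whether it goes under the next visit, under the previous one, or nowhere. The plan also does not state the denominator of each percentage.

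The natural safety question for a new treatment range is what proportion of treated eyes ever had each complication. The planned table does not answer it, and the answer cannot be recovered from visit-specific percentages. Safety is part of the primary objective in section 3.0, and the trial extends treatment beyond the CE-approved range described in section 1.1. If the rule stays open, it may also be settled after the data have been seen.

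**Working it through.** The plan states no complication rate, so there is no planned figure to reproduce. The check is a day count followed by a comparison of the sections.

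**1. Days outside every visit window** (from the section 7.2 windows):
- Between the 1-day and 1-month windows: days 3 to 20, 20 − 3 + 1 = 18 days.
- Between the 1-month and 3-month windows: days 43 to 74, 74 − 43 + 1 = 32 days.
- Between the 3-month and 12-month windows: days 111 to 304, 304 − 111 + 1 = 194 days.
- Total: 18 + 32 + 194 = 244 days.
- Cross-check: the first three windows hold 2 + 22 + 36 = 60 days, and 60 + 244 = 304, the last day before the 12-month window opens.

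This count shows where the missing rule matters. It does not measure how much is missed: the windows are scheduling tolerances, each eye has one scheduled examination in each, and section 8.0 recording continues throughout.

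**2. One event followed through the plan.** Take a grade 2 diffuse lamellar keratitis found on day 5 and resolved before day 21.
- Appendix 1: reportable, with no time limit.
- Section 8.0: inside the recording period, so recorded if the patient reports it or the investigator observes it.
- Item 11, if an event must be present at the visit: counted at no time point.
- Item 11, if events are credited to the next visit: counted at 1 month.

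Both readings fit the text, and they give different tables.

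**3. Why per-visit figures do not give the ever-affected share.** Let n₁ to n₅ be the numbers of eyes shown with a given event at the five time points. The number of distinct eyes among them lies between max(n₁,…,n₅), if the same eyes recur, and the smaller of n₁ + … + n₅ and the number of treated eyes, if all are different. Any between-visit events left unassigned come on top. The planned table cannot say where in that range the truth lies.

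**4. Denominator.** Section 9.2 plans 187 eyes so that 168 remain with follow-up above 90% (168 / 0.90 = 186.7, rounded up to 187). One affected eye is 1/187 = 0.53% of treated eyes, or 1/168 = 0.60% of the eyes expected at 12 months. The difference is small, but the plan does not say which denominator applies.

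**5. Other places where a cumulative measure might be defined.**
- Section 4.2, item 5, reports loss of two or more lines of CDVA, again by time point.
- Section 8.1 keeps patients with surgical complications in the safety investigation and reports, but defines no incidence measure.
- Section 9.1 adds nothing on this point.

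**6. Items that do not carry the point.** For corneal epithelial defect and corneal edema, days 3 to 20 are excluded by Appendix 1 itself, not by the visit gap.

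**The case against.** The strongest reply is that nothing is lost from the data. Patients are told to report any event, the investigator records all events observed, procedure-related events are reported whatever their timing, and Appendix 1 requires every adverse event to be identified on the CRF. Item 11 does not restrict itself to events present on the visit day. The endpoint is descriptive, no test depends on it, and no comparison of complication rates with LASIK is planned: the planned LASIK comparisons concern keratometry and refractive scatter. All of this stands. It makes the point one of tabulation rather than capture, but it does not supply the missing rule or the missing cumulative measure.

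A reader might infer three stronger things that the documents do not support:
- **That between-visit events drop out of the safety percentages.** This requires reading the word *only* into item 11. If such events were credited to the next visit, none would be lost.
- **That a given proportion of acute events would be missed.** Any such figure needs an assumed onset, an assumed duration and the rule that an event must be active at a visit. The documents give none of these. The share of calendar days inside the windows is no substitute, because the windows do not limit recording.
- **That showing a persistent event at two visits is double counting.** In a prevalence table this is correct, and nothing says the percentages will be summed.

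**Conclusion.** The point holds as a gap in the analysis plan, not in data collection. Endpoint 11 summarises complications by visit while recording is continuous. The plan neither assigns between-visit events to a time point nor provides the proportion of treated eyes that ever had each Appendix 1 event. The acute events without a time limit are the ones affected.

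The numerical effect cannot be stated. It is nil for the per-visit counts if between-visit events are carried to the next visit, and of unknown size if they are not. Under either rule the cumulative per-eye figure remains unreported. The conclusion rests only on the wording of sections 4.2, 7.2, 8.0, 8.1 and 9.1 and Appendix 1, and on no assumption about event rates. It is a low-cost improvement to a descriptive endpoint that informs the primary objective.

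**What to change.** Add to item 11, in words such as:

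*For each Appendix 1 event, the number and percentage of treated eyes with at least one occurrence from surgery to the 12-month visit will be reported, based on the continuous adverse event record including unscheduled visits. Each eye counts once per event, the denominator is all treated eyes, and the time limits in Appendix 1 apply. Prevalence at each scheduled visit will be shown in addition, with eyes examined at that visit as denominator.*

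Because the section 8.0 recording period begins after surgery, the text should also say that complications noted on the day of surgery are included. The 6-month limits in Appendix 1 should be reconciled with a schedule that has no 6-month visit.

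The cost is a short addition to the text and one extra table from data already collected. No visit or examination changes. The downside is that the cumulative complication figure may be higher, and so less favourable, than any single visit's percentage.
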